Smoking is a leading cause of death and disease and costs the NHS billions each year. Most smokers want to guit and getting support from publicly funded stop smoking services (SSSs) means they are four times more likely to do so than when they attempt to stop alone. Although around one in every five people is a smoker, SSSs only ever reach around 5-10% of them and numbers attending SSS have been in decline in the last few years. We know that smokers experience lots of barriers to service access that are never addressed (e.g. feeling that they shouldn't need help to stop smoking). With continued pressure on public health funding, it is important to reach and support those most motivated to stop smoking to access available support, so that services can maximise success. It is also important to reach those most likely to experience poor health because of smoking. The 'StopApp', which was designed with help from a group of smokers and ex-smokers, aims to do this. StopApp is a brief, web-based support tool designed to be easily accessible and usable by smokers. It deals with people's barriers to SSS access and allows people to instantly book a SSS appointment, at a time and location to suit them, with text message and email confirmation and reminders. A future trial of this intervention could seek to find out if StopApp is successful at improving SSS bookings and attendance, but there is uncertainty about how easy it would be to recruit people and collect information from them, who would be willing to take part and the best locations to find them. A feasibility (small-scale test) trial is therefore proposed - the MyWay project.

Smoking remains a leading cause of mortality and morbidity worldwide (ASH, 2015). It is the leading cause of preventable death and disease in the UK, accounting for 100 000 deaths per annum (ASH, 2014). In addition, the direct costs of smoking to the NHS have been estimated at between £2.7 billion and £5.2 billion, which is equivalent to around 5% of the total NHS budget each year (Ekpu and Brown, 2015). Stop smoking services (SSSs) provide free and tailored support to help people stop smoking, with the use of pharmacological and behavioural interventions. The services are available to smokers over 12 years of age, including those who are pregnant. The effectiveness of SSSs is judged by the number of smokers who set a guit date and are abstinent from smoking four weeks later, verified as standard by Carbon Monoxide (CO) testing (DH, 2011). Four-week guit rates have been shown to be a reliable predictor of long-term abstinence, with studies showing that collecting further follow-up data at 6 months provides only a modest increase in accuracy (NCSCT, 2014). Based on these measures, smokers who attend SSSs have been found to be four times more likely to guit smoking, than those who attempt to guit alone (West, 2012).

Although most smokers want to guit, and between 22 and 31% of them will make at least one attempt to quit each year (HSCIC, 2014), SSSs currently only reach 5-10% of the smoking population (Dobbie et al., 2015). In addition, despite the effectiveness of SSSs (HSCIC, 2014), relative to the number of smokers, uptake has declined in recent years (Kmietowicz, 2015). This may be explained in part by the recent proliferation of electronic cigarettes (EC) leading people to switch to these instead of guitting smoking or instead of accessing support to guit. However, 95% of SSS practitioners have encountered clients that use EC, suggesting that smokers do not view SSS use and EC as mutually exclusive (Beard et al., 2014). A third of smokers in England have used EC at least once (Brose et al., 2015), and whilst their use is associated with significant reductions in numbers of cigarettes smoked (Brose et al., 2015) this has not led to an overall rise in guit attempts (West and Brown, 2015). Therefore, SSSs are still needed to support guit attempts. Because some EC have recently become regulated, there is now an opportunity for SSSs to integrate this option into the range of nicotine replacement therapy (NRT) they offer. As with other types of NRT (Kotz et al., 2013), the effectiveness of EC in supporting quit attempts is likely to be enhanced with behavioural support from SSSs, and the proliferation of EC need not inhibit SSS access if smokers are aware that services will support their use.

Between 1999 and 2010 in the UK, the Government funded a number of mass media tobacco control campaigns (focussing on the harms of smoking to promote quitting and uptake of SSSs). Suspension of these costly campaigns in 2010 provided an opportunity for a natural experiment to assess the impact they had on behaviour associated with quitting smoking (Langley et al., 2014). Whilst quit line calls, smoke-free web hits and requests for cessation support packs decreased dramatically, there was no effect on attendance at SSSs (Langley et al., 2014). It is therefore unlikely that reintroduction of such campaigns would be an effective intervention for addressing the decline in SSS uptake, and innovative cost-effective approaches to increase SSS uptake are instead required.

Internet based interventions have considerable potential for providing innovative and cost-effective health promotion solutions but concerns are often raised about their potential for disproportionately improving outcomes for those from higher socioeconomic status (SES) groups. Given that smoking contributes considerably to the issue of health inequality (Jha et al., 2006), such concerns require particular attention for online smoking interventions. Research suggests that smokers from lower SES groups *are* being reached by SSS (Kotz and West, 2009)

however variation exists across services (West et al., 2013a). Smokers from the lowest SES groups are half as likely to successfully quit as those from the highest SES grouping, even though they are at least as motivated to guit as those with high SES (Kotz and West, 2009). This significantly increases the chances of poor health outcomes caused by smoking for many of the most vulnerable groups in society (Jha et al., 2006). Interventions designed to address smoking-related behaviours need to ensure that the health inequalities, and where possible, social and environmental inequalities (e.g. access to support and services; presence of smoking in the environment) associated with this issue are addressed. Concerns about the health equity associated with web and app based interventions may not be fully warranted however. Recent research found that a web-based smoking cessation intervention that engaged lower SES groups in development was only effective at supporting smoking cessation in lower SES groups in a randomised controlled trial (Brown et al., 2014). Arguably, a well-designed and well targeted web-based intervention has the potential to contribute to reducing health inequalities associated with smoking, and this potential requires further investigation.

A range of studies conducted since the commissioning of SSSs began, suggest that smokers (in particular those from lower socio-economic status (SES) groups) are often unaware that SSSs exist, or what type of service they offer (Roddy et al., 2006, Benson et al., 2014, Copeland et al., 2010, Ussher et al., 2006, Vogt et al., 2010). Other barriers include negative beliefs about the service including that it lacks efficacy, will be impersonal, judgmental, and not tailored to individual needs (Roddy et al., 2006, Copeland et al., 2010, Benson et al., 2014), Our own research supports these findings and identified that smokers often also feel that needing support to quit smoking is a sign of 'weakness' (Fulton et al., 2016). These barriers to service uptake have not typically been the focus of interventions or health promotion campaigns targeted at smokers, possibly because until recent years access to SSSs had been robust and growing (see Langley et al., 2014). Research has shown however, that booklets explaining the efficacy of services to those who have registered with SSSs can increase attendance rates (Matcham et al., 2014) and that proactively recruiting smokers through GP practices can increase attendance at SSSs and four-week guit rates (Murray et al., 2008). A recent trial (Start2guit) assessing personalised risk information (in the form of a letter from patients' GPs including risk information tailored for any conditions they may have (e.g. heart disease)) and an offer of SSS taster sessions was both effective and cost-effective at increasing SSS uptake (Gilbert et al., 2012, 2016). Given that public health budgets are under increasing pressure, and evidence suggests smokers seeking help themselves are more successful at stopping than those referred by others (Borland et al., 2012), it will become increasingly important that SSSs are used by more of those making guit attempts each year to enhance their chances of success. Implementing inexpensive strategies to help this to happen will maximise effectiveness and costeffectiveness of increasingly tight public health resources.

A handful of other intervention studies have addressed SSS access (Gilbert et al., 2016; 2017; Matcham et al., 2014; Murray et al., 2008), and all have used leaflets or letters from GPs to reach smokers. StopApp is a brief, novel web-based behaviour change intervention, developed with input from smokers from across the SES spectrum that targets the known barriers to service access to improve users' motivation and capability to access SSS. StopApp links to an existing on-line booking system (PharmOutcomes) to provide the opportunity to get a first appointment at SSSs at a time and location to suit the user and could be promoted and accessed across the public health system. Although leaflet and letter based methods are effective, StopApp is unique in that its systematic evidence based development (Fulton et al., 2016; see also detailed description in section 7 below), aimed to address all identified barriers to accessing SSSs whilst also taking account of (or will take account of during evaluation) affordability, practicability, effectiveness (and costeffectiveness), acceptability, side-effects (and safety), and equity (Michie, 2014). The StopApp intervention would likely be delivered at even lower ongoing cost than the cost-effective Start2quit letter and taster session (Gilbert et al 2016; 2017), and if well marketed could reach currently unreached smokers.

A future potential randomised controlled trial will enable us to establish whether and to what extent StopApp is effective and cost-effective at increasing SSS bookings and attendance in comparison to standard methods of recruitment. If effective and cost-effective, it is instantly scalable because PharmOutcomes is used extensively across the UK. Because of the novelty of this intervention, the potential for overlooking health inequalities associated with smoking when using digital interventions, and the limited extant research employing the required trial design across recruitment contexts that replicate real-world use of the intervention (including online and community settings), a feasibility trial is required to establish whether a future RCT can be done and achieved without extensively over-representing or under-representing certain demographic groups.

3. Aims and Objectives

3.1 Aim: The aim of the proposed research is to establish the feasibility and potential health equity of a future randomised controlled trial of the StopApp intervention.

3.2 Primary Objective

To conduct a feasibility trial of StopApp to estimate recruitment and attrition rates of participants across three settings: GP surgeries, community settings and on-line; at baseline, intervention access, and two-month follow-up.

3.3 Secondary Objectives

Secondary objectives of the feasibility trial are to estimate the:

- **3.3.1** acceptability of randomisation and the StopApp intervention for participants
- **3.3.2** acceptability of primary and secondary outcome measures and measures required for cost-effectiveness and cost utility analyses in a future trial
- **3.3.3** key costs which would be incurred in delivering the intervention and usual care, including a comparison of non-attendance at SSS (Did-not-attend or DNA rates) between each arm of the trial.
- **3.3.4** feasibility of accessing SSS and GP data (if recruited via GP) on attendance, quit dates set and four-week quits for trial participants
- **3.3.5** any differential recruitment and attrition rates across socio-economic groups and age and gender
- **3.3.6** rate of SSS attendance in the treatment and control groups to estimate the event rate of the primary outcome measure for a future trial and support future trial sample size calculations

4. Methodology

4.1 Study design

The proposed study is a two-arm parallel group individual participant randomised feasibility RCT of StopApp (intervention) compared with standard promotion of and referral to SSSs (control). The study will also have a nested qualitative process evaluation.

4.2 Setting and Participants

Smokers who are aged 16 years and over will be recruited from 3 settings across Warwickshire including 4 GP surgeries, a range of community settings (e.g. pharmacies, children's centres, libraries) and online. All current smokers aged over 16 years registered with participating GP practices in Warwickshire, or accessing participating community services or viewing advertising for the study online, will be invited to take part in the feasibility trial.

4.3 Recruitment

Recruitment to this feasibility trial is via three settings: GP practices, community settings and online.

4.3.1 GP surgery recruitment

The study is eligible for adoption to the NIHR portfolio and the process of application has begun. We will apply for joint primary care and public health portfolio status. The Clinical Research Network (CRN) are supporting recruitment via GP surgeries. GP practices in Warwickshire have been invited to participate and of those who are interested, we will select four for the feasibility trial (stratified by indices of Deprivation, to ensure we are reaching diverse groups). Patients listed as smokers on the practice records will be checked by practice staff to ensure they meet the inclusion criteria (see 4.4 below) of being aged 16 years or older and a smoker. To remove the chances of contamination, we will contact one smoker per household only. Where two or more smokers cohabit, the resident whose first name is alphabetically first will be selected for invitation to the study and the other resident(s) will receive the control intervention (a web-based pdf with stop smoking service information) after the study has ended. Note: the reason for non-selection will not be provided to the co-habiting smoker to avoid disclosing that the selected resident is a smoker or participating in the study.

Smokers (one smoker per household) will be sent an email and/or text or letter (dependent on GP and patient communications set up) from their GP inviting them to take part in the 'MyWay' study. This will inform them that the study will investigate the best ways of using the internet to help people to stop smoking. Where a GP practice's preferred method of contact with patients is via postal letter, Docmail services will be used to distribute letters as recommended by the CRN. For ethical reasons we will not attempt to recruit people aged less than 16 years as they would typically require parental consent to participate in research and parents may not be aware of their child's smoking status. The email/text/letter (see appendix M & N) will include brief information and a web link/QR code to the study website where further

information and the secure electronic consent process can be accessed (see section 4.9 Procedure below for further information).

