4.10 Questionnaire Measures

4.10.1 Baseline measures

A baseline questionnaire will include questions regarding demographic information (including age, gender, profession, ethnicity, postcode (for purposes of identifying indices of multiple deprivation score)) current smoking status, previous use of SSS, ease of internet access, and motivation to guit, measured using the one item 'Motivation to Stop Scale', MTSS (Kotz et al., 2013) and a single item Likert scale (Hummel et al., 2017). Health-related quality of life data will be collected using the EQ5D-5L instrument to inform the health economic analysis, and the ICECAP-A (ICEpop CAPability measure for Adults) instrument will be used to measure general wellbeing. In addition, we have developed a bespoke resource use questionnaire to gain insight into the costs both to individuals and to the public purse of resources accessed as a result of participation in the study or use of the Stopapp (see appendix E). Participants will be given measures online via the project website. If they register but do not complete baseline measures within two weeks we will send email reminders. Those recruited through GP practices will be sent a reminder (using same method as initially used by GP surgery) two weeks after the first communication. All smokers who agree to take part in the study and return baseline guestionnaire responses will be randomised into either the intervention or control group as described above.

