The main purpose of the proposed feasibility study is to determine whether the main trial can be done. This will largely be determined by whether one or more of the recruitment settings is able to produce the required sample size for a future main trial. Based on the information discussed above we estimate that we need to recruit an average of at least 1.8 participants per day to make a future trial feasible. We will also use data collected about SES, age and gender of those recruited and lost through attrition to understand the health equity of the trial methodology.

7. Research Governance

The nominated sponsor for this research is [name], Associate Pro Vice Chancellor of Research at Coventry University. [name] has confirmed he is prepared to take on sponsorship of the study on behalf of Coventry University. The university has an Information Protection Unit that provides support and information to staff in ensuring they are fully compliant with all Information Governance requirements.

We have a Study Steering Committee (SSC) in place that will operate independently of the research team to assess research governance issues. This includes an independent chair, [name] who is also the public health speciality lead for the West Midlands Clinical Research Network (CRN), [name], a statistician form the Clinical Trials Unit (CTU) at the University of Warwick, members of our PPI group, [name], the tobacco control lead from Public Health Warwickshire, and [name], the tobacco control lead from Public Health England (West Midlands). The SSC will meet at project outset and shortly before each progress report is due to assess progress, data management and research governance issues. All data accessed and retrieved from the SSSs systems will be dealt with on secure servers and stored on password protected files accessible only to members of the research team. We will only seek data for those participants who have provided their expressed consent for us to do so. The outcome measures of this project are routinely collected and recorded by the IT systems in the SSS. The owners of PharmOutcomes and Outcomes4health (Pinnacle Health Ltd) have worked with us to ensure StopApp sends the relevant referral data (only name and mobile telephone number) to the system and stores no data on StopApp itself (user information) that would contravene Information Governance requirements. Instead all data is sent via a secure server to the existing Pinnacle Health system.

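### In GP households with several smokers the invitee is fixed by first name, a non-random rule that could tilt invitations by gender or age

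*Protocol*

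**What the plan says.** Section 4.3.1 (GP surgery recruitment) gives the reason for restricting invitations: "To remove the chances of contamination, we will contact one smoker per household only". For shared households it then fixes the choice: "the resident whose first name is alphabetically first will be selected for invitation to the study". As for those passed over, "the other resident(s) will receive the control intervention" once the study has finished. No random choice within the household is described.

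The study is about who can be recruited. Its aim (section 3.1) is to "establish the feasibility and potential health equity of a future randomised controlled trial", and the rationale just before it asks whether a trial can be run "without extensively over-representing or under-representing certain demographic groups". Objective 3.3.5 is to estimate "any differential recruitment and attrition rates across socio-economic groups and age and gender". Section 6 (Stop/go criteria) returns to this: "We will also use data collected about SES, age and gender of those recruited and lost through attrition" to judge the health equity of the methodology.

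**The concern.** Limiting contamination justifies one invitee per household. It does not justify choosing that person by name. First names are related to gender and, as naming fashions change, to year of birth. In a household with a man and a woman, or with two generations, a rule that sorts on first name may therefore favour one gender or one age group systematically.

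In many trials this would hardly matter. Here the make-up of the recruited group by age and gender is itself a reported result, and the tilt would be introduced by the study's own invitation step. Someone reading the gender mix of GP recruits could take part of it for a difference in willingness when it came from who was asked. The rule is fixed in the protocol as a recruitment procedure, so it is not a detail that an analysis plan would settle later.

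**Working it through.** **1. The plan's own figures.** The protocol gives no figure for the effect of this rule. The GP target used below does reproduce from section 4.11: 980 / (18 × 30 days) = 1.81 per day; 1.8 × 90 days = 162; 162 / 3 settings = 54.

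**2. Inputs that have to be assumed.** The protocol does not say how many listed smokers share a home, or how first names sort by gender. Let
- s = share of listed smokers who live with exactly one other listed smoker, taken as 0.20 to 0.40;
- q = probability that the favoured gender is picked in such a household, taken as 0.55 to 0.60. A random pick has q = 0.50.

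**3. Share of invitees chosen by the rule.** Each pair gives one invitee, so out of every listed smoker s/2 are invited through the rule and 1 − s/2 are invited in total. The share is (s/2) / (1 − s/2).
- s = 0.20: 0.10 / 0.90 = 11.1%
- s = 0.40: 0.20 / 0.80 = 25.0%

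**4. Shift in the gender share of GP invitees** = that share × (q − 0.50). At equal uptake, multiply by 54 for people.

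| s | q | Shift (points) | People among 54 |
|---|---|---|---|
| 0.20 | 0.55 | 0.6 | 0.3 |
| 0.20 | 0.60 | 1.1 | 0.6 |
| 0.40 | 0.55 | 1.25 | 0.7 |
| 0.40 | 0.60 | 2.5 | 1.4 |

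These are upper values for each s and q, because every pair is treated as mixed-sex. A same-sex pair cannot change the gender share.

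**5. A wider range.** Let f be the share of GP invitees who come from mixed-sex two-smoker households. With f from 10% to 40% and q from 0.45 to 0.65, the shift f × (q − 0.50) runs from 0.40 × (−0.05) = −2.0 points to 0.40 × 0.15 = +6.0 points, or about −1 to +3 people of 54. The sign is open. The +6.0 extreme needs s = 2 × 0.40 / 1.40 = 57% of listed smokers paired in this way, which is an extreme assumption.

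**6. Why the denominator should be recorded.** Section 4.12 expresses GP recruitment as a percentage of the smokers found on the practice lists. On that wording, cohabitants who were never asked count as not recruited. If rates by gender were formed on this base, with equal numbers and equal willingness, the fraction invited in each gender would be (1 − s) + s × q for the favoured gender and (1 − s) + s × (1 − q) for the other:
- s = 0.20, q = 0.55: 0.91 v 0.89, ratio 1.02
- s = 0.40, q = 0.60: 0.84 v 0.76, ratio 1.11

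An apparent relative difference of about 2% to 11% would then arise from the rule alone. Section 4.12 plans numbers recruited by gender and does not explicitly plan such rates, so this illustrates the risk and is not an error in a stated analysis.

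**7. After a random pick.** q = 0.50, so the expected shift is 0. The targets of 162 and 54 are unchanged.

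**The case against.** The strongest reply is that the effect is too small to matter. A 50% gender share among 54 people has a 95% interval of about ±1.96 × √(0.25/54) = ±13 points, against a shift of 0.6 to 2.5. Over all three settings the shift is a third of that, about 0.2 to 0.8 points. The rule touches only multi-smoker households in one setting of three. The stop/go rate of 1.8 per day does not depend on it, and the equity data have no threshold. An alphabetical rule is also transparent and simple for practice staff. All of this stands and keeps the point minor. None of it is a reason to prefer a name rule to a random pick, and nothing elsewhere in the protocol corrects it.

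Three stronger readings are tempting and should not be drawn.
- *That the rule distorts the ethnic mix reported under 3.3.5.* That objective names socio-economic group, age and gender only. Ethnicity is collected at baseline (section 4.10.1: "demographic information (including age, gender, profession, ethnicity, postcode"), but every household still yields one invitee, so the ethnic mix can change only where cohabiting smokers differ in ethnicity. By the same logic, a deprivation score taken from a shared postcode cannot move.
- *That invitation and willingness cannot be separated.* They can, if the age and gender of those invited are kept. Practice staff work from patient records, and nothing in the protocol prevents it.
- *That the arms are biased.* Selection precedes consent and allocation, and minimisation uses gender and socio-economic status (section 4.9.2). Minimisation balances the arms; it does not alter who was invited.

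**Conclusion.** The point holds as a minor design improvement. Section 4.3.1 fixes a deterministic, name-based choice for which the stated rationale gives no support, and it could tilt GP invitations on gender or age, both of which objective 3.3.5 reports for recruitment. The size and direction are not derivable from the protocol. Assuming that 20% to 40% of listed smokers live in two-smoker homes and that the rule favours one gender by 55:45 to 60:40, the gender share of GP invitees shifts by at most about 0.6 to 2.5 points. No figure can be put on the age shift. The arm comparison, the sample size and the stop/go recruitment rate are unaffected.

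**What to change.** In section 4.3.1, replace the name rule with a random choice of one smoker per household, made by a random number generated in the practice list export. Have each practice keep counts, by age group and gender, of cohabiting smokers invited and not invited, so that recruitment differences can be described against those who were actually asked.

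The cost is one random-number column and a short aggregate table per practice. It needs no extra contact with patients and no change to the sample size. The contamination safeguard and the undertaking not to tell cohabitants why they were not selected both stay as they are.
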